Official Study Title:

Impact of Sodium-Glucose Co-transporter 2 inhibitors on Cardiovascular System and Anemia in Non-diabetic Chronic Kidney Disease Patients. A Randomized-Controlled Clinical Trial

ClinicalTrials.gov Identifier (NCT Number):

Pending

Document Type:

[Study Protocol / Statistical Analysis Plan]

Document Date:

[April 24, 2022]

Sponsor/Collaborator:

Mansoura Urology and Nephrology Center, Mansoura University, Egypt

Principal Investigator:

[name], MD, PhD

Introduction

Chronic kidney disease (CKD) affects approximately 10% of the adult population worldwide (1). The most common causes of CKD are diabetes, hypertension, and chronic glomerulonephritis (2). Treatment for CKD includes angiotensin converting enzyme inhibitor (ACE-I) / angiotensin II receptor blockers (ARBs), lipid and blood pressure (BP) control (3).

Sodium-glucose co-transporter 2 inhibitors (SGLT2i) are a newly approved class of oral anti-diabetic agents that increase the urinary excretion of glucose, thereby lower blood glucose levels, weight, and blood pressure (4).

There is growing evidence indicating that SGLT2 inhibition is reno-protective. This effect is thought to be achieved partly by mechanisms independent of lowering blood glucose levels (5), such as reduced intra-glomerular pressure through an enhanced tubule-glomerular feedback mechanism (6-7), reduced glucose and sodium transport over the proximal tubular cells (8), increased natriuresis (9) and reduced systemic BP (10-11).

A recent clinical trial (**DAPA-CKD**) showed that SGLT2i treatment reduced the risk of worsening kidney function or death from cardiovascular or kidney disease in patients with chronic kidney disease with and without type 2 diabetes (12).

Also, there are data suggesting SGLT2i acts by inhibiting hepcidin, which will increase iron bioavailability and red blood cell production (13). **Another mechanism is suggested via inducing medullary hypoxia which by turn increases the level of hypoxia inducible factor (HIF) and increase erythropoietin production (14).** These effects on erythropoiesis suggest that the use of SGLT2i reduces the occurrence of anemia. The post-hoc analysis of the CREDENCE trial found that the risk of anemia or the risk of starting anemia treatment in the anemia group of patients with type 2 diabetes and chronic kidney disease was significantly lower than that of the placebo group (15). According to the exploratory analysis of EMPA-REG test data, anemia improvement during SGLT2i treatment was closely related to beneficial cardiovascular outcomes (16).

Dapagliflozin, as a member of SGLT2i family, showed a beneficial effect on cardiovascular outcome (17, 18). As shown in many other trials, Other SGLT2 inhibitors have shown favorable cardiovascular effects, including a reduction in the risk

of hospitalization for heart failure, predominantly in patients with type 2 diabetes and established cardiovascular disease (19-21).

SGLT2 inhibition affects visceral adiposity, glycemic control, hyperinsulinemia, blood pressure, arterial stiffness, and albuminuria (22). Two mechanisms have been proposed as major drivers for beneficial cardiovascular outcome: the diuretic effect associated with SGLT2 inhibition with subsequent hemodynamic unloading of the left ventricle (23) and a shift in cardiac metabolism secondary to increased ketogenesis (24, 25).

Aim of the work

This study aims to:

1. Assess SGT2i role in delaying the progression of ongoing chronic kidney disease.
2. Investigate SGLT2i impact on anemia improvement among non-diabetic CKD patients.
3. Study the impact of SGLT2i on cardiovascular system in these patients.

Research questions

The main research question is: Does use of SGLT2i will show superiority over conventional lines of treatment of chronic kidney disease as regard to efficacy and safety?

Does the use of SGLT2i carry beneficial effect on anemia improvement among these patients?

Does the use of SGLT2i improve cardiac outcome in non-diabetic CKD patients?

Rationale and justification

Dapagliflozin which was originally developed to control blood glucose level in patients with diabetes has recently been shown to have beneficial effects on both the heart and kidney.

Importantly, a large clinical trial has shown dapagliflozin reduced kidney problems. From the way we think the pills work, there is good reason to believe this new medication could benefit people who have kidney disease even they are not diabetic.

To date, there hasn't been a trial that studied the effect of dapagliflozin in terms of anemia improvement only on non-diabetic CKD.

Objectives

The main objective of this study is to:

- Compare use of SGLT2i versus placebo and standard care in regression of chronic kidney disease in non-diabetic CKD patients.
- Study the effect of SGLT2i in decreasing the risk of anemia and improving anemia in non-diabetic CKD patients.
- Study the impact of SGLT2i regarding cardiovascular system.

Hypothesis

Additional therapies to slow kidney function decline are highly desired. The DAPA-CKD trial demonstrated that the sodium glucose co-transporter 2 inhibitor dapagliflozin significantly reduced the risk of kidney failure and prolonged survival in participants with chronic kidney disease with and without type 2 diabetes.

Patients and methods

Study sitting: Urology and Nephrology Center, Mansoura University.

Study design and sample size:

- **Sample size:** was calculated based on previous research by (DAPA-CKD) by (Heerspink et al., 2020) using G. power program with α error 0.05 and power 80% and it was equal to approximately 98 patients.

Type of the study: Randomized controlled trial.

Patients' enrollment: 100 patients with non-diabetic CKD with an estimated glomerular filtration rate (eGFR) of 20-75 ml/min/1.73m² will be randomized into 2 equal groups:

- **Study group:** 50 patients will receive SGLT2i as add on drug, Dapagliflozin 10 mg will be used once daily with or without food.
- **Control group:** 50 patients will receive placebo beside the conventional medications.

All patients will be followed-up for 12 months and their results will be interpreted.

Inclusion criteria:

1. Non-diabetic CKD patients aged more than 18 years.
2. Patient with eGFR > 20 ml/min/1.73m² by 2021 CKD-EPI creatinine equation

Exclusion criteria:

1. eGFR < 20 ml/min per 1.73 m².
2. Medical history of chronic disease (diabetes mellitus, chronic liver disease, bladder cancer, severe respiratory distress).
3. Evidence of urinary obstruction or difficulty in voiding at screening.
4. Receiving high dose diuretics or combined ACEI and ARB.
5. History of recurrent urinary tract infection.

6. Active infection including TB and HIV.
7. Current or previous organ transplantation or expected to get a kidney transplant within 12 months.
8. Patients who are on SGLT2i for more than the preceding 3 months.

Study design:

Study Protocol:

- Patients included in the study will be treated with dapagliflozin initiated at a single daily morning dosage of 10 mg/day.

Methods:

The following data will be collected and evaluated for all patients:

I-Baseline investigations:

- Patients of both groups will be subjected to full history taking including duration of CKD and drug history and routine clinical examination.
- Ankle/brachial pressure index (ABPI) to assess peripheral vascular disease.

➤ Laboratory investigations:

- 1) Serum creatinine, Creatinine clearance.
- 2) Urine analysis.
- 3) 24-hour urine protein and/or spot urine protein/creatinine ratio.
- 4) Random blood glucose.
- 5) Lipid profile
- 6) Iron profile tests:

- Hemoglobin
- Mean corpuscular volume (MCV) and Hematocrit (Hct).
- Serum ferritin
- Transferrin saturation (TSAT)
- Serum hepcidin level
- Serum erythropoietin level.

7) B-type natriuretic peptide (BNP) level.

➤ **Cardiovascular investigatory tools:**

- Electrocardiography (ECG).
- Echocardiography to assess myocardial function.

➤ **Radiological investigations:**

- Agatston score using CT scan: for assessment of coronary calcification.

1. II-Post-intervention investigations:

All patients will be evaluated every visit (every 3 months) regarding:

- Regular measurement of blood pressure each visit.
- Ankle/brachial pressure index.
- Laboratory investigations:
 - 1) Serum creatinine, creatinine clearance.
 - 2) Urine analysis.
 - 3) 24-hour urine protein and/or spot urine protein/creatinine ratio.
 - 4) Fasting blood glucose.
 - 5) Lipid profile.

6) Iron profile (Hemoglobin, MCV, hematocrit, ferritin, TSAT,)

All patients will be evaluated at 12 months regarding:

➤ Ankle/brachial pressure index.

➤ **Laboratory investigations:**

1) Serum creatinine, Creatinine clearance.

2) 24-hour urine protein and/or spot urine protein/creatinine ratio.

3) Urine analysis.

4) Fasting blood glucose.

5) Lipid profile.

6) Iron profile tests:

- Hemoglobin
- Mean corpuscular volume (MCV) and Hematocrit (Hct).
- Serum ferritin
- Transferrin saturation (TSAT)
- Serum hepcidin level
- Serum erythropoietin level.

➤ **Cardiovascular investigatory tools:**

- Electrocardiography (ECG).
- Echocardiography to assess myocardial function.

➤ **Radiological investigations:**

- Agatston score using CT scan: for assessment of coronary calcification.

Outcomes:

Primary outcome measures:

- Time to the first occurrence of any of the components of the composite:
≥50% sustained decline in eGFR, reaching end-stage kidney disease.
[Time Frame: 12 months]

Secondary outcome measures:

- Effect of Dapagliflozin on eGFR.
- Effect of Dapagliflozin on anemia & erythropoietin level.
- Effect of Dapagliflozin on myocardial function and coronary calcifications.
- Safety of Dapagliflozin regarding the number of hypoglycemia episodes between groups and serious adverse events.

Statistical Analysis:

Qualitative data will be displayed in cross tabulations, and quantitative data will be described in terms of arithmetic mean \pm SD. Bivariate techniques will be used for initial evaluation of contrasts. Thus, the chi-square and Fisher's exact tests will be used for comparisons of frequencies of qualitative variables; the Mann-Whitney test and the unpaired t-test will be used for comparisons of means of two quantitative variables. A p-value ≤ 0.05 is considered significant. Patient survival rates will be assessed using the Kaplan-Meier method. All analyses will be carried out using the computer package SPSS for windows, release 21 SPSS Inc. Chicago, III, USA.

Administrative design

All the patients provided written informed consent before study entry and the approval was obtained from institutional review board (MS.22.04.1973) in Faculty of Medicine, Mansoura University. There is no funding.

References

1. Eckardt, K. U., Coresh, J., Devuyst, O., Johnson, R. J., Köttgen, A., Levey, A. S., & Levin, A. (2013). Evolving importance of kidney disease: from subspecialty to global health burden. *The Lancet*, 382(9887), 158-169.
3. Silver, S. A., Bell, C. M., Chertow, G. M., Shah, P. S., Shojania, K., Wald, R., & Harel, Z. (2017). Effectiveness of quality improvement strategies for the management of CKD: a meta-analysis. *Clinical Journal of the American Society of Nephrology*, 12(10), 1601-1614.

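### The anaemia objective has two parts, but the outcome is one undefined line analysed without baseline haemoglobin, so resolution and prevention of anaemia cannot be told apart

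*Combined protocol and SAP*

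**What the plan says.** - **Objectives:** the second item is to "Study the effect of SGLT2i in decreasing the risk of anemia and improving anemia in non-diabetic CKD patients". Anaemia is also in the trial's title.
- **Aim of the work:** the second aim names improvement only: "Investigate SGLT2i impact on anemia improvement among non-diabetic CKD patients". The matching research question also asks only about improvement.
- **Eligibility:** the two inclusion criteria are "Non-diabetic CKD patients aged more than 18 years" and "Patient with eGFR > 20 ml/min/1.73m² by 2021 CKD-EPI creatinine equation". No inclusion or exclusion criterion mentions haemoglobin or anaemia.
- **Allocation:** 100 patients "will be randomized into 2 equal groups". No stratification is described.
- **Secondary outcome measures:** the only anaemia entry is "Effect of Dapagliflozin on anemia & erythropoietin level". It has no haemoglobin cut-off, metric, time point or at-risk population.
- **Post-intervention investigations:** the 3-monthly list includes "6) Iron profile (Hemoglobin, MCV, hematocrit, ferritin, TSAT". Haemoglobin is also listed at baseline and at 12 months.
- **Statistical Analysis:** chi-square or Fisher's exact test for frequencies, and the t-test or Mann-Whitney test for quantitative variables. There is no adjustment for a baseline value and no analysis by baseline anaemia status.

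**The concern.** The two halves of the objective apply to different patients. A haemoglobin rise in someone who was never anaemic is not an improvement of anaemia. Anaemia already present at entry is not a new case. With no haemoglobin criterion, the trial will probably enrol both kinds of patient, which a two-part objective needs, but the outcome and analysis then do not distinguish them.

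Two things are at stake. First, a favourable whole-arm result could be reported as improving anaemia, as lowering its risk, or as both, with the cut-off, metric and subset chosen after the data are seen. Second, with 50 patients per arm the proportion anaemic at entry can differ noticeably by chance, and an unadjusted comparison leaves that difference in the 12-month result.

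**Working it through.** **Inputs.** From the documents: 100 patients, 50 per arm, 12 months, haemoglobin at baseline and every 3 months. The documents give no share anaemic at entry, no resolution rate and no rate of new anaemia, so every rate below is an assumption. There is no anaemia figure to reproduce. The sample size of about 98 has no stated effect size and plays no part here.

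**1. A whole-arm frequency does not separate the two effects.** Assume 25 anaemic and 25 non-anaemic patients per arm. The number anaemic at 12 months is 25 × (1 − resolution) + 25 × new-anaemia rate.

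| Arm | Resolution | New anaemia | Anaemic at 12 months |
|---|---|---|---|
| Control | 20% | 20% | 20 + 5 = 25 of 50 (50%) |
| Drug, improvement only | 40% | 20% | 15 + 5 = 20 of 50 (40%) |
| Drug, prevention only | 20% | 0% | 20 + 0 = 20 of 50 (40%) |
| Drug, more new anaemia | 64% | 44% | 9 + 11 = 20 of 50 (40%) |

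The three drug rows give the same whole-arm result. In the last, lowering the risk of anaemia would be the reverse of what happened.

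**2. Chance imbalance at entry.** Assume 40 of 100 anaemic and unstratified 50:50 allocation. The number anaemic in one arm is hypergeometric (100, 40, 50) with mean 20. P(16 or fewer) = 0.076, so the probability of a 16:24 split or worse in either direction is 2 × 0.076 = 0.15.

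Take a 16:24 split with no drug effect, 20% resolution and 10% new anaemia in both arms:
- Arm with 16 anaemic: (16 × 0.80 + 34 × 0.10)/50 = 16.2/50 = 32.4%.
- Arm with 24 anaemic: (24 × 0.80 + 26 × 0.10)/50 = 21.8/50 = 43.6%.
- Gap: 11.2 points.

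**3. What the split analyses could show.** Assume resolution of 40% on drug and 20% on control, and new anaemia of 5% and 10%. With share p anaemic at entry, whole-arm prevalence at 12 months is p × (1 − resolution) + (1 − p) × new-anaemia rate. Power (two-sided 0.05, pooled-variance normal approximation, n per arm) is Φ{[|p1 − p2| − 1.96 √(2p̄(1 − p̄)/n)] / √[(p1(1 − p1) + p2(1 − p2))/n]}. For example, resolution with n = 15 gives Φ[(0.20 − 0.328)/0.163] = Φ(−0.78) = 0.22.

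| Share anaemic | Anaemic / not, per arm | Anaemic at 12 months, control vs drug | Difference | Power, whole arm | Power, resolution | Power, new anaemia |
|---|---|---|---|---|---|---|
| 30% | 15 / 35 | 31.0% vs 21.5% | 9.5 | 19% | 22% | 12% |
| 40% | 20 / 30 | 38.0% vs 27.0% | 11.0 | 21% | 28% | 11% |
| 50% | 25 / 25 | 45.0% vs 32.5% | 12.5 | 25% | 33% | 10% |
| 60% | 30 / 20 | 52.0% vs 38.0% | 14.0 | 29% | 39% | 9% |

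An unpooled-variance approximation moves these subset powers by no more than about two points.

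**4. Imbalance together with an effect.** Use the same rates at 40% anaemic, where the balanced difference is 11 points. With 24 anaemic on drug and 16 on control: drug (24 × 0.60 + 26 × 0.05)/50 = 31.4%, control 32.4%, difference 1 point. With the split reversed: drug (16 × 0.60 + 34 × 0.05)/50 = 22.6%, control 43.6%, difference 21 points. The imbalance moves the result by about 10 points either way.

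**The case against.** The strongest reply is that a randomised comparison of all patients is legitimate. It estimates the average effect on haemoglobin or anaemia prevalence in the population enrolled, and lower prevalence on drug would be a real benefit. The Introduction's rationale, through hepcidin and erythropoietin, concerns red-cell production in general, so mean haemoglobin in everyone is a coherent target. This stands. A reader might infer that a whole-arm analysis answers neither part of the objective and is worthless. The documents do not support that. Its limit is that it cannot attribute the effect to resolution or to prevention.

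It is also fair to say that the plan never assigns a test, metric or population to anaemia. The whole-arm analysis is inferred from generic tests, which the Statistical Analysis section introduces as an initial evaluation. What is documented is an undefined outcome and no stated use of baseline haemoglobin, not a deliberate choice to pool.

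Chance imbalance is not systematic bias. Randomisation balances the arms on average, and an unadjusted test's error rate already allows for imbalance. A reader might set the 16-point baseline difference (24 versus 16 of 50) against the 11-point effect and conclude that imbalance outweighs the effect. Those are unlike quantities. On the 12-month scale the carry-through is about 10–11 points, roughly the size of the illustrative effect. The 0.15 counts both directions; an imbalance that large against the drug has probability 0.076.

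Finally, splitting the sample costs precision, and the analysis of new anaemia would be close to uninformative under the assumed rates. That is a reason to label the subset analyses exploratory. It does not justify leaving the outcome undefined until the data are seen.

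**Conclusion.** The point holds in a limited form. The objective promises two anaemia effects, the outcome does not distinguish them, and the described analyses make no use of baseline haemoglobin although it will be measured. A whole-arm comparison would be valid for the average effect, but it would not support a specific claim of improving anaemia or of lowering its risk. Without adjustment it would also be noisier than necessary: in the illustration, an imbalance with probability 0.15 shifts 12-month prevalence by about 10–11 points.

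All sizes rest on assumed rates. The inability to separate resolution from prevention does not. Anaemia is a secondary outcome, so the primary analysis is unaffected. But it is in the title and the objectives, and the correction is cheap, so it should be made.

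**What to change.** 1. Make the key anaemia analysis the whole-arm haemoglobin comparison adjusted for continuous baseline haemoglobin, by ANCOVA at 12 months or a mixed model over the 3-monthly values. State which.
2. Fix one haemoglobin cut-off for anaemia before the data are examined. Prespecify two further analyses, both labelled exploratory:
   - haemoglobin change and resolution of anaemia in patients anaemic at baseline, for the improvement claim;
   - first occurrence of anaemia in patients not anaemic at baseline, for the risk claim.

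   Limit each claim to its own result.
3. Reconcile the improvement-only Aim with the two-part Objective.

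Stratifying randomisation by baseline anaemia is optional, since adjustment for baseline haemoglobin deals with chance imbalance in the key analysis.

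**Cost:** a short amendment, with no new test, visit or patient. The downside is imprecision in the two subset analyses. Under the illustrative rates, with 30–60% anaemic at entry, power is about 22–39% for resolution and 9–12% for new anaemia. The plan should state this, so that a null subset result is not read as evidence of no effect.

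### The 98-patient calculation cannot be reproduced, and its 80% power does not hold for the 12-month kidney composite at assumed control risks of 5–30% and hazard ratios of 0.5–0.7

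*Combined protocol and SAP*

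**What the plan says.** Under Patients and methods (Study design and sample size), the sample size "was calculated based on previous research by (DAPA-CKD"), "using G. power program with α error 0.05 and power 80% and it was equal to approximately 98 patients". The plan then enrols 100 non-diabetic patients, 50 per arm, and follows them for 12 months. Significance level, power, software and source trial are given. Outcome, effect size, event risk or standard deviation, test, sidedness and dropout are not.

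Under Outcomes there is one primary outcome: "Time to the first occurrence of any of the components of the composite", the components being "≥50% sustained decline in eGFR, reaching end-stage kidney disease", with "Time Frame: 12 months".

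The Statistical Analysis section does not fill the gap. For time-to-event data it says only "Patient survival rates will be assessed using the Kaplan-Meier method" and names no between-group test. For categorical data, chi-square and Fisher's "exact tests will be used for comparisons of frequencies of qualitative variables". The threshold is "A p-value ≤ 0.05 is considered significant", again without sidedness.

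**The concern.** A reader will take the 80% to refer to the primary outcome, because no other outcome is named beside it. A time-to-event comparison draws its power from events, not patients. One year of follow-up in 100 patients can give few events on an outcome as severe as a sustained halving of eGFR or end-stage kidney disease.

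Naming the source trial does not supply the missing inputs. As the Introduction describes that trial, its result also covered cardiovascular and kidney death, and its patients included people with type 2 diabetes. This composite has no death component and this population has no diabetes, so figures for that result would not carry over unchanged.

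The stake is how the result will be read. Delaying progression of kidney disease is the first aim, and the main research question is one of superiority. A non-significant composite reported beside a claimed 80% power invites the conclusion that the drug does not help the kidney, when the data may be unable to say.

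**Working it through.** **1. Trying to reproduce the 98.** A forward calculation is impossible without an effect size, so I solved backwards at α 0.05 and 80% power. Several unrelated input sets give about 98:

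- Two-sided comparison of means, standardised difference 0.57: n per arm = 2(1.960 + 0.842)²/0.57² ≈ 48.3, so 49 per arm and 98 in total.
- One-sided comparison of means: standardised difference about 0.50–0.51.
- Two-sided comparison of proportions: 30% v 7.9%, or 20% v 2.3%.

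The figure therefore identifies no particular calculation.

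**2. Power for the composite.** Inputs from the plan: 50 per arm, 12 months, α 0.05. My assumptions, because the plan gives none: 12-month control risk p of 5–30%, HR of 0.5–0.7, proportional hazards, no dropout.

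- Risk on drug = 1 − (1 − p)^HR
- Expected events D = 50 × (p + risk on drug)
- Power (Schoenfeld) = Φ(|ln HR| × √D / 2 − z), with z = 1.960 two-sided or 1.645 one-sided

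Example, p = 10% and HR 0.6: risk on drug = 1 − 0.9^0.6 = 6.13%; D = 50 × 0.1613 = 8.06; power = Φ(0.511 × 2.84/2 − 1.960) = Φ(−1.23) = 10.8%.

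Two-sided power in %, with a log-rank simulation in brackets (exponential event times, censoring at 12 months, 10,000 runs per cell):

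| Control risk | HR 0.5 | HR 0.6 | HR 0.7 |
|---|---|---|---|
| 5% | 9.9 (7.6) | 7.4 (6.6) | 5.6 (5.3) |
| 10% | 15.7 (14.3) | 10.8 (10.1) | 7.5 (8.0) |
| 15% | 21.5 (20.3) | 14.2 (13.7) | 9.3 (10.1) |
| 20% | 27.2 (25.7) | 17.6 (16.9) | 11.1 (11.1) |
| 30% | 38.5 (37.1) | 24.4 (23.5) | 14.7 (14.2) |

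Expected events run from 3.8 (5%, HR 0.5) to 26.0 (30%, HR 0.7).

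**3. Other readings of the plan.**

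- One-sided α: 10.1–50.9%.
- Fisher's exact test on 12-month proportions: 0.8–29.0%.
- An assumed 10% dropout, simulated, two-sided: 10.1% (10%, HR 0.6), 16.5% (20%, HR 0.6), 35.2% (30%, HR 0.5).

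**4. What would rescue the 80%.** Events needed, two-sided: 4(1.960 + 0.842)²/(ln HR)², which is 66, 121 and 247 at HR 0.5, 0.6 and 0.7.

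- HR 0.5: a control risk of about 78% gives D = 50 × (0.78 + 1 − 0.22^0.5) = 65.5. One-sided, about 63% is enough.
- HR 0.6 and 0.7: with an event in all 100 patients, power is Φ(0.511 × 10/2 − 1.960) = 72% and Φ(0.357 × 10/2 − 1.960) = 43% (82% and 56% one-sided).
- Stronger effects, by two-sided log-rank simulation: HR about 0.25 at 30% control risk, 0.15 at 20% and 0.07 at 15%. At 10%, zero events on drug gives about 75%.

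**5. Precision.** At HR 0.6, SE(ln HR) = √(1/d_control + 1/d_drug).

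- 10% risk: 5.0 and 3.06 events, SE 0.726, expected 95% interval 0.14–2.49.
- 20% risk: 10.0 and 6.27 events, SE 0.509, expected 95% interval 0.22–1.63.

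**The case against.** The arithmetic is not in dispute; what may be concluded from it is.

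- **The power range is conditional.** Both the control risks and the hazard ratios are mine. This stands, and is why the values that would rescue the 80% are given as well. The entry criteria set no proteinuria or recent-decline threshold and exclude eGFR below 20, so I find no ground in them for a risk above 30%. They do not settle the risk either.
- **The 98 may belong to another outcome**, such as a continuous one with a standardised difference near 0.57. That is possible, but then the 80% was never a statement about the primary outcome, and the plan should say so.
- **A kidney-only or non-diabetic figure may have been taken from the source trial.** The Hypothesis section credits that trial with reducing kidney failure, so this cannot be excluded. It is a reason to state which figure was used.
- **The approximation is weak at about 4 events.** True: 9.9% by formula against 7.6% simulated in one cell. The simulated range over the grid, about 5–37%, leads to the same conclusion.
- **No passage says that a null result will be read as no benefit.** Correct; the misreading is a risk, not a stated intention.
- **Reporting an estimate needs a method that the plan lacks.** This stands. At 5% control risk the chance that at least one arm has no event is 0.95^50 + 0.95^25 − 0.95^75 = 33% at HR 0.5, and 0.95^50 + 0.95^35 − 0.95^85 = 23% at HR 0.7. An ordinary interval for the hazard ratio would then not exist. The fix allows for this.

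**Conclusion.** The concern holds. The 98 cannot be reproduced, because apart from α and power none of the inputs that determine it is stated. No miscalculation is shown.

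The stated 80% does not hold for the only primary outcome over control risks of 5–30% and HR 0.5–0.7. Between 61% and 94% of such trials would be non-significant, two-sided, although the drug works. No one-sided, exact-test or dropout variant examined over those ranges rises above about 51%. Reaching 80% needs a one-year control risk, or a treatment effect, far outside the ranges assumed here.

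The percentages rest on assumed risks and hazard ratios, proportional hazards and, in the main grid, no dropout, which favours the trial. That the inputs are missing rests on no assumption.

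**What to change.** Keep 100 patients and the primary outcome, and replace the sample-size sentence.

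1. State the outcome, effect size, test, sidedness and dropout behind the 98, and which figures came from the source trial.
2. Give expected events and power for the composite at 100 patients, from a stated and sourced 12-month control risk and hazard ratio for non-diabetic patients, checked by simulation. For illustration only: a 10–20% risk with HR 0.6 gives about 8–16 events and 11–18% two-sided power.
3. Unless that calculation reaches 80%, say that the composite is not powered at 80% and will be reported as an estimate with a confidence interval, and that a non-significant result will not be read as evidence of no kidney benefit.
4. Add to Statistical Analysis how the estimate is obtained. Kaplan-Meier 12-month risks by arm and their difference would serve, with an interval method that stays usable when an arm has no events.

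The cost is a rewritten paragraph, one short calculation and a sentence in the analysis section, with no extra patients or procedures. The drawback is that the stated power for the composite will probably look much less favourable.

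### No stratification by entry eGFR is described and no planned analysis uses it, although the primary composite probably depends on it

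*Combined protocol and SAP*

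**What the plan says.** Under Patients' enrollment, patients with "eGFR) of 20-75 ml/min/1.73m² will be randomized into 2 equal groups" of 50 each. Neither that paragraph nor any other gives a sequence-generation method, blocking, minimisation or a stratification factor. The inclusion criterion reads "Patient with eGFR > 20 ml/min/1.73m² by 2021 CKD-EPI creatinine equation", so eGFR is measured before allocation. That criterion has no upper limit, while the enrolment text stops at 75.

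The primary outcome is "Time to the first occurrence of any of the components of the composite", with components "≥50% sustained decline in eGFR, reaching end-stage kidney disease", over 12 months. ESKD is given no eGFR value and no other definition.

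The Statistical Analysis section lists chi-square, Fisher, Mann-Whitney and unpaired t-tests, and Kaplan-Meier for patient survival. It names no stratified or covariate-adjusted comparison. Entry eGFR is therefore handled neither at allocation nor in the analysis.

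**The concern.** The first component is a halving of the patient's own entry value, and the second is a state that is normally tied to an absolute level of kidney function. A patient entering near 20 is close to both. A patient entering at 75 must lose 37.5 ml/min/1.73m² in a year. If risk differs strongly across the range and the arms happen to receive unequal numbers of low-eGFR patients, part of the observed difference reflects entry eGFR rather than dapagliflozin. With 50 patients per arm and few events, one or two misplaced events change the estimate visibly, and a model-based adjustment chosen afterwards would be fragile.

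**Working it through.** **The plan's own figure.** The sample size statement ("was calculated based on previous research by (DAPA-CKD"; "α error 0.05 and power 80% and it was equal to approximately 98 patients") cannot be reproduced, because no effect size or event rate is stated. A total of 98 fits, among others, a standardised difference of 0.57 (two-sided t-test), 20% versus 2.2-2.5%, or 30% versus about 8%. It therefore does not show how many events were expected, or in whom.

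**Inputs from the plan.** Entry eGFR 20-75, 50 per arm, 12 months, a 50% decline threshold.

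**Assumptions, because the plan is silent.** Entry eGFR uniform on 20-75; the size and shape of the 12-month decline; the ESKD cut-off.

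**1. Loss needed for an event.** A 50% decline needs a loss of 0.5 × entry. If ESKD were eGFR below 15, that component needs a loss of entry − 15.

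| Entry eGFR | Loss for 50% decline | Loss to reach 15 |
|---|---|---|
| 20 | 10 | 5 |
| 25 | 12.5 | 10 |
| 30 | 15 | 15 |
| 50 | 25 | 35 |
| 75 | 37.5 | 60 |

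With a cut-off of 15, the absolute threshold is reached first below 30 and the relative one above 30. A cut-off of 10 adds nothing, because half of any entry value above 20 is still above 10.

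**2. Share of events from entry below 30.** This group is (30 − 20)/(75 − 20) = 18% of patients. Simulated results:

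| Assumed 12-month decline | ESKD cut-off | Share of events |
|---|---|---|
| Same ml/min at every entry value: mean 4-6, SD 6-8 | none, 10 or 15 | 67-92% |
| Proportional: mean 10%, SD 20-25% | 15 | 35-46% |
| Proportional: mean 10%, SD 20-25% | none or 10 | about 18% |

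In the first row the overall event rate is 1.8-7.7%, and the risk is 8-32% below 30 against 0.4-2.3% above. In the second row the risks are 8.5-13.1% against 2.3-5.5%. In the third row risk does not depend on entry eGFR. The simulation counts a single 12-month value as an event and ignores the requirement that the decline be sustained, so it may overstate the risks.

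**3. Chance of an uneven split.** With 18 of 100 patients below 30 and a fixed 50:50 allocation, P(k in one arm) = C(18,k) × C(82,50−k) / C(100,50). Summing over k ≤ 6 and k ≥ 12 gives 0.19. With 10 such patients, a 7:3 or worse split has probability 0.32.

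**4. Effect of a 12:6 split with no treatment effect.** The expected event difference is 6 × (risk below 30 − risk above 30).
- Risks of 28% and 2%: 6 × 0.26 = 1.6 events. By arm this is 12 × 0.28 + 38 × 0.02 = 4.1 against 6 × 0.28 + 44 × 0.02 = 2.6.
- Risks of 8% and 0.4%: 6 × 0.076 = 0.5 events.
- Proportional decline with a cut-off of 15: 6 × (0.085 − 0.023) = 0.4 to 6 × (0.131 − 0.055) = 0.5 events.
- Proportional decline with no effective absolute cut-off: 0.

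**5. False-positive rate.** With 18 patients at 20-40% risk and the rest at 1%, the unadjusted chi-square test rejects a true null as follows.

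| Split of the 18 | Rejection rate |
|---|---|
| 9:9 | 1.8-3.1% |
| 12:6 | 5.8-8.5% |
| 13:5 | 8.2-15.1% |
| Average over all splits | 4.3-4.6% |

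Fisher's test averages 0.5-1.5%. At risks of 28% and 2% it rejects in 2.0% of null trials at 12:6 and 3.3% at 13:5.

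**The case against.** A reader might infer that almost all events must come from patients near the eGFR floor, so that chance imbalance there can decide the primary result. The documents do not support this, for three reasons.

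- The concentration depends on assuming the same ml/min decline at 20 as at 75. Under proportional decline it weakens or disappears, and the plan has no data to choose between the two. The absolute threshold is itself assumed, because ESKD is undefined.
- Randomisation without stratification is valid. Average type I error stays at or below 5%, and the p-value already allows for chance imbalance. With 50 per arm, 5 versus 0 events gives Fisher p = 0.056, and it takes 6 versus 0 (p = 0.027) to reach significance.
- It would also go too far to say that the allocation is not balanced on eGFR. The method is unstated, and the supportable statement is that no stratification is described.

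The objection adds that stratification cannot rescue a comparison with so few events, and that is correct.

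All of this limits the size of the point but does not remove it. In every scenario examined with an ESKD cut-off of 15, entry eGFR remains prognostic: 2.4 to 3.7 times the risk below 30 even under proportional decline. False-positive rates conditional on the split differ clearly although their average is sound. The variable is already in hand at screening, and the plan uses it nowhere.

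**Conclusion.** The point holds as a design improvement that should be made. The plan describes no stratification by entry eGFR and no analysis that uses it, for an outcome built on eGFR. The harm falls on the estimate, its precision and its interpretation in the one trial that will be run. It does not fall on the overall error rate.

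The size is conditional. A 12:6 or worse split has a probability of about 19%, given 18 patients below 30. Such a split shifts between 0 and about 1.6 expected events across the worked cases, and the upper figure compares with about 3.3 expected per arm (9 × 0.28 + 41 × 0.02). These figures rest on a uniform entry distribution, on the assumed shape of decline and on the assumed ESKD cut-off. The small number of expected events is a separate and larger problem.

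**What to change.** 1. State the randomisation method, and use permuted blocks stratified by screening eGFR, for example below 30 versus 30 or above by the 2021 CKD-EPI equation already used for eligibility.
2. Name a primary comparison that uses the stratum, for example a stratified log-rank test.
3. Report primary events by arm within stratum, so that readers can see which part of the entry range the result comes from.
4. If enrolment has begun, allocation already made cannot be changed. Prespecify the stratified comparison and the by-stratum report before unblinding.

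The cost is two randomisation lists instead of one and a few lines of text, with no extra test or patient. Incomplete blocks may leave the arms one or two patients away from exactly 50:50.
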